1.1. ESR1 mutations and endocrine resistance

Acquired mutations in *ESR1* (20-30%) have been described in metastatic breast cancer (MBC) patients exposed to estrogen deprivation with aromatase inhibitors (AI) [2-5]. *ESR1* mutations are uncommon in primary breast cancers and rarely observed after adjuvant AI suggesting clonal selection[6]. Though, recent studies have suggested that de novo *ESR1* mutations might be observed at low allele frequencies [7, 8]. Currently the use of AI or AI in combination with cyclin-dependent kinase (CDK) 4/6 inhibitors are recommended for first line treatment of ER positive MBC. Constitutive activation, through mutations in the ligand-binding domain (e.g. Y537S, D538G, S463P), leads to AI resistance and portend a shorter survival [6]. Though, these mutations may exhibit sensitivity to selective estrogen receptor down-regulators (SERD) (e.g. fulvestrant) that target mutant ER for proteasomal degradation[9]. In the BOLERO-2 study, which tested the use of exemestane alone or in combination with everolimus in MBC with prior exposure to AI, plasma *ESR1* mutations (D538G and Y537S only) were identified in nearly 30% of patients. While *ESR1* mutations were associated with shorter overall survival compared to wildtype (32 months), Y537S *ESR1* mutations (20 months) were associated with a worse outcome compared to D538G (26 months) suggesting differences in the variants [10]. In SoFEA trial, which compared the activity of fulvestrant versus exemestane against fulvestrant in combination with anastrozole in hormone-receptor (HR) positive metastatic postmenopausal women who had progressed on prior non-steroidal AI, plasma *ESR1* mutations were observed in nearly 40% of patients. In PALOMA-3 study, which evaluated the addition of CDK 4/6-inhibitor palbociclib to fulvestrant, approximately 25% of patients were found to harbor *ESR1* mutations in plasma, which did not appear to be predictive of palbociclib response. The lower prevalence of *ESR1* mutations in PALOMA3 likely reflects the inclusion of patients with primary resistance to endocrine therapy and prior tamoxifen exposure.

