treatment efficacy with ability to transition from an ineffective therapy to a potentially active one. Furthermore, mutational allele frequency (MAF) represent tumor clones harboring a mutation, thus providing an indicator of tumor burden. Serial monitoring of MAF with ctDNA in patients treated with targeted therapies has been shown to be associated with time to radiologic disease progression [16]. Clatot et al. retrospectively analyzed *ESR1* mutations in ctDNA in patients who were treated with AI for MBC as first line [17]. *ESR1* mutations were identified in 31% of patients at progression with AI. Patients with *ESR1* mutations had worse median PFS (5.9 months) compared to patients without a mutation (7 months). In patients with *ESR1* mutations, 75% of them had detectable circulating mutations before clinical progression. Also, patients presenting with increases in circulating *ESR1* at 3 months after subsequent treatment with prior AI had disease progression. In the FERGI study, patients with radiologic response (complete or partial) demonstrated significant decreases in *ESR1* plasma MAF post treatment with fulvestrant and these were detected early in the course of response. ctDNA analysis of NSCLC patients treated with EGFR inhibitors, showed that EGFR T790M, a common mechanism of secondary resistance ctDNA was detected nearly 2 months prior to clinical progression and that the EGFR T790M ctDNA positive patients had significantly shorter survival [18]. ctDNA velocity with decrease in MAF at 6 weeks were shown to be predictive of response and associated with improved survival to durvalumab in lung cancer [19]. Similarly, in the study evaluating the efficacy of neratinib in advanced breast cancer patients with ERBB2 mutations, decrease in MAF at 4 weeks was predictive of clinical response [20].

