9. STATISTICAL CONSIDERATIONS

Primary/Secondary Objectives:

This is a randomized, open-label, Phase II, for HR positive advanced breast cancer patients who have been treated with AI and CDK as first line in the metastatic setting for at least 12 months and who have *ESR1* mutations identified through ctDNA assay.

[name], MS, Department of Biostatistics at MD Anderson Cancer Center, will oversee the implementation of the statistical analysis. The primary endpoint is PFS, which is measured from the date of study randomization to the date of event (ie, death and/or disease progression) or the date of last follow-up if no event has occurred. Survival curves for PFS will be analyzed using the Kaplan-Meier method and survival difference across groups will be examined by log rank test. Patients alive and disease-free at the latest clinical evaluation will be censored for PFS at the date of that evaluation. We will estimate the treatment comparison with 95% confidence intervals and p-value using Cox proportional hazards regression and we will assess the proportional hazard assumption using graphs of rescaled Schoenfeld residuals and related tests. We would attempt to identify independent predictors of PFS using multivariable Cox PH regression analysis. Analysis for OS and PFS from the start of next line of therapy will be performed as described for PFS from the date of randomization. Randomization will be performed using Core. Stratification factors include recurrence free interval (\leq 3 years vs. $>$ 3 years), prior adjuvant endocrine therapy (tamoxifen vs. aromatase inhibitor), and site of metastasis (bone vs. visceral).

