To detect a change in median PFS from 5 months (for AI arm) to 9 months (with fulvestrant arm) would require about 124 patients (assuming 4-5 patients per month accrual, 5 months post-accrual follow-up, 5% two-sided alpha, 80% power, log rank testing). 84 PFS events are expected under the alternative hypothesis. Interim analysis will be performed when 42 PFS events are observed. Using O'Brien-Fleming stopping boundaries, we will stop for futility if the log rank test p-value $>$ 0.72 and stop for success if it is $<$ 0.004. Descriptive statistics and graphical analysis will be used to summarize patients' demographic and clinico-pathological characteristics, and efficacy outcomes. We will use mean (standard deviation) or median (range) to summarize continuous variables and frequency (percentages) for categorical variables. Graphical analysis, such as scatter plots with Lowess smoothers, will be used to assess the correlative structure of outcomes and compare MAF between fulvestrant and AI treated groups. The Pearson correlation, or its non-parametric analogue, the Spearman correlation, will be used to estimate the linear correlation among variables. Radiographic response rate (partial response + complete clinical response) will be estimated and reported with a 95% CI.

Control	Experimental	
Median	Median	Power
5	6	15%
5	7	38%
5	8	63%
5	9	81%
5	10	91%
5	11	96%
5	12	98%

REFERENCES:

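### The PFS treatment comparison names no covariates, although baseline ESR1 allele fraction and variant are known before randomisation; pre-specified adjustment would be a cheap but uncertain gain in power

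*Combined protocol and SAP*

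**What the plan says.** Section 9 (Statistical Considerations) describes the primary PFS analysis in three steps.

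- Test: "survival difference across groups will be examined by log rank test".
- Estimate: "We will estimate the treatment comparison with 95% confidence intervals and p-value using Cox proportional hazards regression". No covariates are listed.
- Further modelling: "We would attempt to identify independent predictors of PFS using multivariable Cox PH regression analysis". No covariates are listed here either, and the model has no stated role in the treatment comparison.

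The randomisation factors start with "Stratification factors include recurrence free interval" and also cover prior adjuvant endocrine therapy and site of metastasis. ESR1 MAF and variant are not among them. The trial is sized on the log-rank test: "To detect a change in median PFS from 5 months (for AI arm) to 9 months (with fulvestrant arm") "would require about 124 patients". The interim boundaries at 42 events (p > 0.72 for futility, p < 0.004 for success) are defined on the same test.

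Section 8 makes ctDNA testing compulsory before randomisation, and inclusion criterion 5 requires an activating ESR1 mutation found on it. The variant is therefore known for every randomised patient, and in practice so is the MAF.

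On the value of these measures, Section 1.2 says "mutational allele frequency (MAF) represent tumor clones harboring a mutation, thus providing an indicator of tumor burden". For Y537S, Section 1.1 gives overall survival as "20 months) were associated with a worse outcome compared to D538G (26 months) suggesting differences in the variants".

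**The concern.** If a baseline covariate is strongly prognostic, leaving it out of a Cox model pulls the estimated hazard ratio toward 1 and lowers log-rank power. Adjusting for it restores that power at the same sample size. It also removes the effect of a chance difference in tumour burden between arms of about 62.

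The rationale in Section 1.6 is to act while disease burden is minimal, so a measure linked to burden is a natural candidate. The data come from the test that makes the patient eligible, so no extra sample is needed.

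Timing matters because the trial is open-label. An adjusted estimate is convincing only if its covariates are fixed before outcomes are seen. The planned search for predictors cannot serve that purpose.

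**Working it through.** **1. The plan's own power.** Inputs from Section 9: medians 5 and 9 months, 124 patients, accrual 4-5 per month, 5 months' further follow-up, two-sided 5%. Assumed because not stated: 1:1 allocation, exponential PFS, no dropout.

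At 5 per month, accrual lasts A = 124/5 = 24.8 months, F = 5 and λ = ln 2/median. The event probability is 1 − [exp(−λF) − exp(−λ(A+F))]/(λA).

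- AI: λ = 0.1386, probability 0.859, 62 × 0.859 = 53.3 events.
- Fulvestrant: λ = 0.0770, probability 0.697, 62 × 0.697 = 43.2 events.
- Total: 96.5 events.

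Schoenfeld power = Φ(√96.5/2 × ln(9/5) − 1.96) = Φ(4.912 × 0.588 − 1.96) = Φ(0.93) = 82.3%. The Section 9 table gives 81%, so the figure reproduces.

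The 84 events quoted in Section 9 would give Φ(√84/2 × 0.588 − 1.96) = 76.8% if that were the final count. What 84 means is a separate question; step 4 shows that this point does not depend on it.

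**2. Strength of the covariates.** For the variant, 26/20 = 1.3 as a hazard ratio if survival is exponential. This is overall survival in a trial of exemestane with or without everolimus, carried over to PFS here as an assumption. For baseline ESR1 MAF the documents give no hazard ratio, so a range is assumed.

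**3. Simulated power.** There were 8,000-10,000 trials per case, at 4.5 per month, with marginal medians fixed at 5 and 9 and no interim. Log MAF was normal and the variant was split 50:50 (assumed). The comparison is the unadjusted log-rank against the Wald test from Cox with both covariates. Simulation error is about 0.4-0.5 points per figure.

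| Variant HR | MAF HR per SD (assumed) | Log-rank | Adjusted | Change (points) | Unadjusted HR |
|---|---|---|---|---|---|
| 1.0 | 1.0 | 82.3% | 81.8% | −0.5 | 0.555 |
| 1.3 | 1.0 | 82.7% | 82.6% | −0.1 | 0.555 |
| 1.3 | 1.2 | 80.1% | 81.5% | +1.4 | 0.564 |
| 1.3 | 1.5 | 74.1% | 80.8% | +6.7 | 0.586 |
| 1.3 | 2.0 | 62.3% | 79.4% | +17.1 | 0.621 |

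A second simulation gave 82.7% to 81.9% with nothing prognostic, 80.8% to 82.5% at 1.22 per SD, and 73.2% to 80.4% at 1.5. Adding three further uninformative covariates to a model in which nothing is prognostic gave 82.9% to 81.4%.

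**4. Sensitivity to the set-up.** Fixing both medians fixes the conditional hazard ratio at 5/9, so the log-rank falls as heterogeneity grows. If the marginal hazard ratio is held near 5/9 instead (5 per month), the log-rank stays near 80% and the adjusted test rises: 80.7% to 80.0% with nothing prognostic, 80.7% to 82.5% at 1.2 per SD, 79.8% to 85.8% at 1.5. With the analysis cut at 84 events, the same three cases give 75.7% to 75.1%, 73.2% to 75.0%, and 68.3% to 74.6%. The change from adjustment is similar in all three set-ups.

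**5. Chance imbalance.** The between-arm difference in mean log MAF has SD √(2/62) = 0.18 in SD units. A gap of 0.3 or more, in either direction, is 0.3/0.18 = 1.67 standard errors, so it occurs in about 9-10% of trials. At an assumed 1.5 per SD it shifts the hazard ratio by 1.5^0.3 = 1.13, for example from 0.556 to 0.63.

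**6. Type I error (two-sided, nominal 5%).** At the final analysis, the two-covariate Wald test rejected 5.2-5.4% of the time against 5.0-5.1% for the log-rank; a further run gave 5.0%. At 42 events it rejected 5.5-5.8%. With five covariates at 42 events it rejected 6.3-6.7%, against 5.1-5.2% for the log-rank. At the 0.004 boundary the five-covariate test rejected 0.50-0.52% against 0.40-0.44%, which is within simulation error.

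**The case against.** An unadjusted log-rank test is a standard and valid primary analysis for a randomised phase II trial, and nothing in the documents contradicts it. Stratifying by bone versus visceral disease already captures some of the tumour burden. The simulations contain no stratification factors, so they do not show what MAF adds once site is known. Both objections stand: this is a question of efficiency, not of validity.

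A reader might infer several stronger things that the documents do not support.

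- **That the protocol presents both measures as prognostic for PFS.** It does not. The variant figure is overall survival in another setting. For MAF there is the tumour-burden statement, and the breast and lung cancer findings that Section 1.2 goes on to describe concern change on treatment. The only baseline allele-frequency statement is a reference title about lung cancer and overall survival.
- **That the power is free.** Uninformative covariates cost some power, the primary test changes, and the hazard ratio has a different meaning.
- **That the trial falls short of its planned power.** The log-rank drops well below 80% only under an assumed strong MAF effect with both medians held at 5 and 9.
- **That Section 9 rules out adjustment.** It is silent.
- **That the adjusted test can simply replace the log-rank at both looks.** With many covariates and 42 events, the Wald test rejects somewhat too often.

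**Conclusion.** The point holds as a worthwhile improvement of uncertain size. No covariate is named for the PFS comparison, and two candidates are measured before randomisation at no extra cost.

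The variant alone, at the only strength the documents allow (about 1.3), adds nothing visible. Any useful gain must come from MAF: about 1 to 2 points of power at 1.2 per SD and about 7 at 1.5. If neither is prognostic, the two covariates cost about 0.5 to 1 point. Protection against chance imbalance also depends on MAF being prognostic.

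These figures rest on 1:1 allocation, exponential PFS given the covariates, no dropout, no interim stop, and assumed MAF strengths that the documents neither support nor exclude. The 2.0 row shows the direction at an extreme and should not be used as a forecast.

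**What to change.** In Section 9, before outcomes are seen:

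- Make the final-analysis treatment estimate and test a Cox model with treatment, log10 baseline ESR1 MAF and Y537S present/absent, alongside any stratification terms adopted.
- Define MAF as the highest ESR1 MAF on the screening Guardant360. A fixed rule is needed because Section 1.2 reports polyclonal mutations and criterion 5 admits novel alterations.
- Report the unadjusted log-rank and hazard ratio as supportive.
- Keep the log-rank at the 42-event interim, where the p > 0.72 and p < 0.004 boundaries are defined. The alternative is a score or likelihood-ratio test with few covariates, which was not simulated here and should be checked at 42 events first.
- State the final significance level with the two different statistics in mind. Spending 0.004 at the interim and 0.05 − 0.004 = 0.046 at the end is safe whatever their correlation.
- Keep the search for independent predictors exploratory.

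The cost is wording, since the screening data already exist. The downside is up to about 1 point of power if MAF and variant carry no information (82.9% to 81.4% in the run with three more uninformative terms), and a hazard ratio that is conditional on the covariates. The sample size need not change.

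### If the trial stops for success at 42 events, the plain Cox hazard ratio will tend to overstate the benefit and its 95% interval will under-cover; Section 9 has no rule for reporting that case

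*Combined protocol and SAP*

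**What the plan says.** Section 9 plans one interim look: "Interim analysis will be performed when 42 PFS events are observed". The rule is to "stop for futility if the log rank test p-value $>$ 0.72 and stop for success if it is $<$ 0.004", described as O'Brien-Fleming boundaries.

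For the effect estimate, the same section says: "We will estimate the treatment comparison with 95% confidence intervals and p-value using Cox proportional hazards regression". It applies this to PFS without separating a trial that stops at the interim from one that runs to its end.

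Section 9 is the whole statistical plan. It mentions no bias-adjusted estimate, no interval or p-value that allows for the interim look, and no caution about results after an early stop. It also gives no allocation ratio and no significance level for the final analysis.

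**The concern.** A success boundary at half the stated events lets through only extreme results. A trial that stops there has been selected for a large observed effect, so the ordinary Cox HR tends to exaggerate the benefit. The ordinary 95% interval, computed as if no selection had taken place, misses the truth more often than its label says.

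The HR and interval would be what readers take from a stopped trial, and nothing in the plan would warn them. The power table in Section 9 runs from a 6-month to a 12-month experimental median, so effects smaller than the planned one are contemplated. For smaller effects, an early success is rarer but more misleading.

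**Working it through.** **Inputs from Section 9.** Medians of 5 months (AI) and 9 months (fulvestrant), so HR = 5/9; N = 124. The design terms are "assuming 4-5 patients per month accrual, 5 months post-accrual follow-up, 5% two-sided alpha, 80% power, log rank testing". The stated event count at the planned effect is 84. The interim is at 42 events, with success at p < 0.004 and futility at p > 0.72.

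**Assumptions.** 1:1 allocation, exponential PFS, no dropout, variance of log HR = 4/events, and a final test at two-sided 0.05. P-values are read as two-sided unless stated.

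**Step 1: reproduce the plan's figures.** With 124 patients at 5 per month, accrual lasts 124/5 = 24.8 months. With 5 more months of follow-up, about 96.5 events are expected if the trial never stops early. Integrating over the interim result gives:

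| Experimental median (months) | 6 | 7 | 8 | 9 | 10 | 11 | 12 |
|---|---|---|---|---|---|---|---|
| Plan, power % | 15 | 38 | 63 | 81 | 91 | 96 | 98 |
| Recomputed, power % | 14.5 | 37.9 | 62.8 | 80.7 | 90.9 | 95.9 | 98.2 |

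The average event count, allowing for early stopping, is 84.8 against the stated 84. As a fixed total, 84 events would give only Φ(0.588 × √84/2 − 1.96) = 76.8% power. So 84 fits best as an average. Steps 2 to 5 depend only on the 42 interim events.

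**Step 2: the HR needed for early success.** SE = 2/√42 = 0.309. Two-sided p = 0.004 gives z = 2.878. The boundary log HR is −2.878 × 0.309 = −0.888, so HR = 0.411.

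**Step 3: how often it happens.**
- True HR 5/9 = 0.556: log HR/SE = −0.588/0.309 = −1.905. P = Φ(−2.878 + 1.905) = Φ(−0.973) = 16.5%.
- True HR 0.70: −0.357/0.309 = −1.156. P = Φ(−1.722) = 4.25%.

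**Step 4: the average reported HR given early success** (truncated normal, geometric mean).
- True HR 0.556: −0.588 − 0.309 × φ(0.973)/Φ(−0.973) = −0.588 − 0.464 = −1.052, so HR = 0.35.
- True HR 0.70: HR = 0.36.

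**Step 5: coverage of the plain 95% interval given early success.** The interval errs towards too much benefit with probability 0.025. At these true HRs, all such results lie beyond the boundary.
- True HR 0.556: 1 − 0.025/0.165 = 85%.
- True HR 0.70: 1 − 0.025/0.0425 = 41%.
- True HR above about 0.75: 0%, because the interval on the boundary already ends at 0.75.

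A check with 20,000 simulated trials fitted by Cox regression gave HR 0.33 and coverage 86% at a true HR of 0.556, and HR 0.35 and 44% at 0.70.

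**Step 6: all outcomes, stopped or not.** Overall coverage for true HRs of 0.556 to 0.70, across final analyses at 84 and at 96.5 events:

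| Reading of the futility rule | Coverage |
|---|---|
| Two-sided p > 0.72 | 93.9-94.9% |
| Directional: stop unless z favours fulvestrant by more than 0.358 | 93.1-93.5% |
| One-sided p > 0.72 | 92.0-94.2% |
| No futility stop | 93.5-94.6% |

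At a true HR of 1, coverage is about 95%. Under the two-sided rule the overall average HR is 0.54 when the truth is 0.556, and 0.709 when it is 0.70. Type I error, with 84 final events, is 4.96% if the two-sided futility rule is followed and 5.14% if it is ignored.

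**Step 7: what the remedies do after an early success.**
- *Repeated interval* (log HR ± 2.878 SE). At an observed HR of 0.411 it is 0.17-1.00, against the plain 0.22-0.75. Given early success it covers 1 − 0.002/0.165 = 98.8% at a true HR of 0.556, and 1 − 0.002/0.0425 = 95.3% at 0.70.
- *Mean-bias-adjusted HR.* An observed 0.411 becomes about 0.44, and 0.35 becomes about 0.37.
- *Stagewise-ordered interval and median-unbiased HR.* After a stop at the first look these equal the plain result, so they change nothing here.

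**The case against.** The strongest reply is that a 95% interval promises coverage over all repetitions of the trial, not within the subset that stops early. Over all repetitions the loss is about one point at the planned effect under the two-sided futility reading, which is the reading that reproduces the power table. Any design with early stopping shows low conditional coverage, and plain Cox results after one conservative look are a common choice in a phase II trial of this size. The available corrections are also imperfect: the bias adjustment moves the HR only slightly, and the repeated interval over-covers at the planned effect. All of this stands. It limits the point to the early-success report and argues against replacing the primary analysis.

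It does not remove the point. About one trial in six would stop early even if the planning assumption were exactly right, and the plan gives readers of that report no warning.

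A reader might infer more than the documents support:
- *The 95% interval is generally invalid.* It is not; Step 6 shows modest losses overall.
- *The stopping decision is unsound.* The decision uses the log rank boundaries, and type I error stays near 5%.
- *Either kind of stop inflates the benefit.* A futility stop does not.
- *The estimate will mis-size a confirmatory trial.* The documents mention no such trial.
- *The plan rules out adjustment.* It is silent on the matter.

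**Conclusion.** The point holds as a gap in reporting. If the trial stops for success at 42 events, the only result that Section 9 names is a plain Cox HR. At the planned effect this averages about 0.35 against a truth of 0.556, with an interval that covers about 85% of the time. At a true HR of 0.70 the interval covers about 41% of the time, but that situation arises in only about 4% of trials.

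The early-success figures rest on 1:1 allocation, the usual large-sample variance of the log HR, and a two-sided reading of p < 0.004. They do not depend on the futility reading or on the final event count. The overall figures depend on both, within the ranges shown, and on a final test at 0.05, which the plan does not state.

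**What to change.** Keep the Cox analysis as primary. Add to Section 9, before the interim is run, that if the trial stops for success at 42 events the report will show beside the plain Cox result:

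1. a repeated confidence interval using the interim critical value, 2.88 in place of 1.96;
2. a bias-adjusted HR, with the method named;
3. a statement that an HR from an early stop is likely to overstate the benefit.

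Do not rely on stagewise-ordered or median-unbiased inference for this purpose.

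The cost is a few lines of text and a short calculation. Sample size, visits and boundaries do not change. The downside is a wider interval that is conservative at the planned effect and, for a result on the boundary, reaches 1.00 by construction. The bias adjustment is small, so the written caution has to do part of the work. The rule should be fixed in advance, because an adjustment chosen after seeing a striking HR would carry little weight.

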The investigator (or physician designee) is responsible for verifying and providing source documentation for all adverse events and assigning the attribution for all adverse events for subjects enrolled.

Protocol #2018-0287 will be monitored by the MD Anderson External Data and Safety Monitoring Board (EDSMB).

Laboratory test abnormalities

Laboratory abnormalities that constitute an adverse event in their own right (are considered clinically significant, induce clinical signs or symptoms, require concomitant therapy or require changes in study treatment), should be recorded on the Adverse Events CRF. Whenever possible, a diagnosis, rather than a symptom should be provided (e.g. anemia instead of low hemoglobin). Laboratory abnormalities that meet the criteria for Adverse Events should be followed until they have returned to normal or an adequate explanation of the abnormality is found. Laboratory abnormalities, that do not meet the definition of an adverse event, should not be reported as adverse events. A Grade 3 or 4 event (severe) as per CTCAE does not automatically indicate a SAE unless it meets the definition of serious as defined below and/or as per investigator's discretion. Grade 3 or 4 neutropenia is an expected, on-target, AE with CDK4/6 inhibitors. Thus, dose modifications for neutropenia should follow specific prescribing information brochure guidelines.

Recommended Adverse Event Recording Guidelines

Attribution	Grade 1	Grade 2	Grade 3	Grade 4	Grade 5
Unrelated	Phase I				

		Phase II		Phase II	
				Phase III	Phase III
Unlikely	Phase I	Phase I	Phase I	Phase I	Phase I
			Phase II	Phase II	Phase II
				Phase III	Phase III
Possible	Phase I	Phase I	Phase I	Phase I	Phase I
	Phase II	Phase II	Phase II	Phase II	Phase II
		Phase III	Phase III	Phase III	Phase III
Probable	Phase I	Phase I	Phase I	Phase I	Phase I
	Phase II	Phase II	Phase II	Phase II	Phase II
		Phase III	Phase III	Phase III	Phase III
Definitive	Phase I	Phase I	Phase I	Phase I	Phase I
	Phase II	Phase II	Phase II	Phase II	Phase II
		Phase III	Phase III	Phase III	Phase III

Pregnancy

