6.2. Evaluation during study

Follow up laboratory assessments should be performed as per standard of care for palbociclib, ribociclib, abemaciclib, and fulvestrant

- Physical examination (including vital signs, weight, performance status)
- Patients will undergo restaging with complete imaging (CT CAP and bone scan) approximately every 3-4 cycles of therapy for the first 12 months and every 3-6 months thereafter until progression.
- Exploratory ctDNA blood draws (Guardant360 StreckTM cell preservation tubes (8-10 mL x 2 per blood draw) will be performed at Cycle 2, Cycle 4 and Cycle 12. These will be banked at MDACC. ctDNA will be drawn on the same date as standard of care labs assessments.
- End of Treatment/Progression ctDNA Blood draw (Guardant360 StreckTM cell preservation tubes (8-10 mL x 2 per blood draw).

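### The interim stopping rules carry no direction: read two-sided, a neutral result stops for futility, most results favouring AI continue, and an extreme AI win counts as success

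*Combined protocol and SAP*

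**What the plan says.** Section 9 (Statistical Considerations) contains the only formal stopping rule. "Interim analysis will be performed when 42 PFS events are observed", O'Brien-Fleming boundaries are named, and then: "we will stop for futility if the log rank test p-value $>$ 0.72 and stop for success if it is $<$ 0.004". Nothing says whether these p-values are one- or two-sided, which arm must be ahead, or whether futility is binding.

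The design assumptions are "assuming 4-5 patients per month accrual, 5 months post-accrual follow-up, 5% two-sided alpha, 80% power, log rank testing". The target is a median PFS of 5 months on AI and 9 months on fulvestrant, with about 124 patients. The section adds that "84 PFS events are expected under the alternative hypothesis". The primary test is a log-rank comparison of the arms with no direction given, and the allocation ratio is not stated.

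Section 5.4 names an external data and safety monitoring board but gives it no directional or harm rule.

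**The concern.** A two-sided p-value measures distance from no difference and ignores which arm is ahead. A futility rule that fires when p is large therefore stops the trial near HR 1 and lets it continue as the result moves away from HR 1 in either direction, including against fulvestrant. A success rule that fires when p is small is met by an extreme result for either arm.

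The trial asks whether switching to fulvestrant prolongs PFS. For that question, a worse interim result for fulvestrant should never make continuation more likely. Under the literal rule it does. At stake are the decision at 42 events and the patients who would still be randomised after it.

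**Working it through.** **Inputs.** From Section 9: 42 interim events, cut-offs 0.72 and 0.004, two-sided 5% alpha, 124 patients, 4-5 per month, 5 months of further follow-up, medians 5 and 9 months. Assumed: 1:1 allocation, exponential PFS and Z ~ N(d, 1), with d = -ln(HR) x sqrt(42/4) and sqrt(10.5) = 3.240. Positive Z favours fulvestrant.

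**1. The plan's own figures.** At 5 patients per month, 124 patients give 96.5 events at full follow-up under 5 versus 9 months. Two-look power was computed by numerical integration, with the interim at 42 events and final |Z| > 1.96:

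| Fulvestrant median (months) | 6 | 7 | 8 | 9 | 10 | 11 | 12 |
|---|---|---|---|---|---|---|---|
| Plan's table (%) | 15 | 38 | 63 | 81 | 91 | 96 | 98 |
| Two-sided cut-offs, literal | 14.7 | 38.0 | 62.8 | 80.7 | 90.9 | 95.9 | 98.2 |
| Signed Z, futility below 0.36 | 14.3 | 37.7 | 62.5 | 80.5 | 90.8 | 95.9 | 98.2 |
| One-sided cut-offs | 15.6 | 40.0 | 65.0 | 82.5 | 92.1 | 96.7 | 98.6 |

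Expected events at 5 versus 9 months, allowing for early stopping, are 84.8 (literal) and 84.1 (signed), against the stated 84. The plan's figures fit cut-offs on the two-sided scale and do not fit one-sided cut-offs. They cannot separate the literal rule from a signed one.

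The success cut-off points the same way. At half information, O'Brien-Fleming gives a two-sided p of 0.0052 (classical) or 0.0031 (Lan-DeMets). A value of 0.004 lies between these, whereas a one-sided 0.004 would be two-sided 0.008.

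**2. Cut-offs as hazard ratios.**
- Two-sided p > 0.72: |Z| < 0.3585, so HR = exp(±0.3585/3.240) = 0.895 to 1.117.
- Two-sided p < 0.004: |Z| > 2.878, so HR < 0.411 or HR > 2.431.
- No stop: HR 0.411 to 0.895, and HR 1.117 to 2.431.
- Inside the adverse gap: HR 1.3 gives p = 0.40, HR 1.5 gives p = 0.19 and HR 2.0 gives p = 0.025.
- One-sided p favouring fulvestrant: futility at Z < -0.583 (HR > 1.197), success at Z > 2.652 (HR < 0.441).
- With 2:1 allocation the two-sided adverse limits become 1.124 and 2.565.

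**3. Interim probabilities.** Literal futility is Phi(0.3585 - d) - Phi(-0.3585 - d). Signed futility is Phi(0.3585 - d). The one-sided reading is Phi(-0.583 - d). AI meets the success rule with probability Phi(-2.878 - d). Continuing in the adverse gap is Phi(-0.3585 - d) - Phi(-2.878 - d).

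| True HR | Futility, literal | Futility, one-sided reading | Futility, signed | AI result meets success | Continue at observed HR 1.12-2.43 |
|---|---|---|---|---|---|
| 1.0 | 28% | 28% | 64% | 0.2% | 36% |
| 1.3 | 20% | 61% | 89% | 2.1% | 67% |
| 1.5 | 12% | 77% | 95% | 5.9% | 77% |
| 1.8 | 5% | 91% | 99% | 16.5% | 77% |

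Counting both rules, the literal plan stops in 22%, 18% and 21% of cases at HR 1.3, 1.5 and 1.8.

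**4. Patients still to enrol.** Take an AI median of 5 months, a true HR of 1.5 and 4-5 patients per month. At the 42nd event, 64-69 patients are enrolled with no scan delay, 70-76 if progression is found at 12-week scans, and 72-79 at 16-week scans (Section 6.2 sets imaging "approximately every 3-4 cycles of therapy for the first 12 months"). That leaves 124 - 79 = 45 to 124 - 64 = 60 patients to be randomised.

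**The case against.** **A symmetric plan is legitimate.** A two-sided design may stop for no difference at small |Z| and for either arm at large |Z|, and the primary objective in Section 2.1 is worded neutrally. However, the hypothesis closing Section 1.2 is that early intervention improves survival, and the sample size is built on 5 to 9 months in favour of fulvestrant. An inner futility window suits a trial that wants to show either arm superior, which this trial does not set out to do.

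**The sponsor may have planned a signed rule and reported only its p-value.** This stands as a possibility, because the power table and the 84 events fit both. It bears on intent; the written rule still lacks the sign.

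**Wrong-direction success is mostly a label.** This largely stands. Stopping at such a result is a reasonable action, no false claim for fulvestrant follows, and the probability at HR 1.0 is 0.2%. The adverse gap is the more practical fault.

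**Harm is unlikely, and the board can use judgement.** The fulvestrant data cited in Section 1.4 do point towards benefit, and the HRs of 1.3 to 1.8 are scenarios, not forecasts. Yet with no true difference the trial still continues inside the adverse gap 36% of the time. The board may depart from the text, but the text gives it no directional rule to apply. The count of 45 to 60 patients also assumes that accrual could stop on the day of the 42nd event.

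**Conclusion.** The concern holds. On the two-sided reading, which is the only sidedness stated and the scale that the plan's figures fit, the futility rule covers observed HRs of 0.90 to 1.12. Nothing stops the trial between 1.12 and 2.43 against fulvestrant, and a result above 2.43 counts as success. At a true HR of 1.5, futility stopping is 12%, against 95% for the same cut-off on a signed Z.

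The HR limits assume 1:1 allocation; at 2:1 they move only to 1.12 and 2.57. The sponsor's intent cannot be settled from the documents. A one-sided reading would restore direction but is not stated and fits the figures less well.

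**What to change.** State both rules in Section 9 on a signed log-rank Z, positive favouring fulvestrant, and repeat them in the monitoring board's charter:
- Success if Z > 2.88, that is, two-sided p < 0.004 with HR below 1.
- Non-binding futility if Z < 0.36, which includes every result favouring AI.

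Name the O'Brien-Fleming version and the allocation ratio. If a one-sided p favouring fulvestrant was meant, say so and re-check 0.004 against the boundary.

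**Power and type I error.** With the final critical value set for 5% two-sided ignoring futility (1.976 at 98.6 events, 1.972 at 84), power at 5 versus 9 months goes from 81.0% to 80.8% with 98.6 final events (accrual at 4.5 per month), and from 75.6% to 75.5% with 84. Type I error does not rise: with 98.6 events the upper-tail error is 2.34% if the signed futility rule is followed and 2.5% if it is ignored.

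**Futility stopping.** The change is one sentence, but it alters how often the trial stops when benefit is nil or small:

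| Scenario | Literal | Signed |
|---|---|---|
| No difference | 28% | 64% |
| 5 vs 6 months | 24% | 41% |
| 5 vs 7 months | 16% | 23% |
| 5 vs 9 months | 4.9% | 6.1% |

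The sponsor should accept these rates or choose a lower signed cut-off. For example, Z < -0.58 keeps futility stopping at 28% under no difference and still stops 77% of the time at a true HR of 1.5.
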